### **8.1.5 Chronic urticaria quality of life questionnaire**

The CU-Q2oL is a disease-specific instrument used to assess the QoL in adult participants with CSU (34). The CU-Q2oL is a 23-item, self-administered questionnaire that includes 6 QoL dimensions: pruritus, swelling, impact on life activities, sleep problems, limits, and looks. Each item is scored on a 5-point Likert scale (1 = not at all, 5 = extremely) where participants indicate how troubled they are within each dimension. The individual items are summed to generate the overall CU-Q2oL score, which is then converted to a 0 to 100 scale; higher scores indicate greater QoL impairment.

Participants will complete the CU-Q2oL as described in the SoA (Section 1.3). The assessment tool is provided in Section 10.7.6.

### **8.1.6 Patient Global Impression of Change of CSU disease and Patient Global Impression of Severity of CSU disease**

The Patient Global Impression of Change (PGIC) is a 1-item questionnaire that asks the participant to provide the overall self-assessment of change in their CSU on a 7-point scale, compared to just before participant started taking the study treatment. Response choices are: 0 = "Very much better", 1 = "Moderately better", 2 = "A little better", 3 = "No change", 4 = "A little worse", 5 = "Moderately worse", 6 = "Very much worse".

The Patient Global Impression of Severity (PGIS) is a 1-item questionnaire that asks participants to provide the overall self-assessment of their participant's disease severity on a 4-point scale for the past week. Response choices are: 1 = "none", 2 = "Mild", 3 = "Moderate", 4 = "Severe".

Participants will complete the 2 items as described in the SoA (Section 1.3). The items are provided in Section 10.7.7 and Section 10.7.8.

### **8.1.7 EuroQOL 5 dimensions questionnaire**

The Euroqol-5 dimensions (EQ-5D) is a standardized PRO measure of health status developed by the EuroQOL Group in order to provide a simple, generic measure of health for clinical and economic appraisal. The adult version of the questionnaire is adapted to patients aged 16 and older. The EQ-5D consists of 2 parts: the descriptive system and the EQ visual analogue scale (EQ VAS). The EQ-5D 5L descriptive system comprises the following 5 dimensions: mobility, self-care, usual activities, pain/discomfort, and anxiety/depression. Each dimension has 5 levels of perceived problems: “no problem”, “slight problems”, “moderate problems, severe problems, and inability to do the activity (35). The respondent is asked to indicate his/her health state by ticking (or placing a cross) in the box against the most appropriate statement in each of the 5 dimensions; this results in a 1-digit number expressing the level for that dimension. The digits for 5 dimensions can be combined in a 5-digit number describing the respondent’s health state. The EQ VAS records the respondent’s self-rated health on a vertical, VAS where the endpoints are labeled “best imaginable health state (100)” and “worst imaginable health state (0)”. This information can be used as a quantitative measure of health outcome as judged by the individual respondents.

The EQ-5D Youth version (EQ-5D Y) will be administered to children  $\geq$ 6 to  $<$ 12 years old and adolescents 12 to 15 years old (36). The EQ-5D-Y is based on the EQ-5D-3L and essentially consists of 2 pages: the EQ-5D descriptive system and the EQ VAS. The EQ-5D-Y descriptive system comprises the following 5 dimensions: mobility, looking after myself, doing usual activities, having pain or discomfort and feeling worried, sad or unhappy. Each dimension has 3 levels: no problems, some problems and a lot of problems. The EQ VAS records the younger patient’s self-rated health on a vertical VAS where the endpoints are labelled “The best health you can imagine” and “The worst health you can imagine”.

Participants will complete the questionnaire as described in the SoA ([Section 1.3](#)). The assessment tool is provided in [Section 10.7.9](#) and [Section 10.7.10](#).

### **8.1.8 Missed school/work days**

Participants who are employed or enrolled in school will be asked to report the number of sick leave/missed school days since the last study assessment.

Participants will complete the questionnaire as described in the SoA ([Section 1.3](#)). The assessment tool is provided in [Section 10.7.11](#).

## **8.2 SAFETY ASSESSMENTS**

Planned time points for all safety assessments are provided in the SoA ([Section 1.3](#)).

### **8.2.1 Physical examinations**

- A complete physical examination will include skin, nasal cavities, eyes, ears, respiratory, cardiovascular, gastrointestinal, neurological, lymphatic, and musculoskeletal systems.
- Investigators should pay special attention to clinical signs related to previous serious illnesses.
- Any new finding or worsening of previous finding should be reported as a new adverse event.

### **8.2.2 Vital signs**

- Vital signs will be measured in a semi-supine or sitting position after 5 minutes rest and will include axillary or oral temperature (same method of temperature measurement should be used during the course of the study), systolic and diastolic blood pressure, and pulse and respiratory rate. Blood pressure and pulse measurements should be assessed using the same arm with a completely automated device. Manual techniques will be used only if an automated device is not available.
- Body weight (kg) will be measured at screening (Visit 1) and at EOT/EOS visits. Height will be measured at screening visit (Visit 1). Height and weight should be measured with indoor clothing but without shoes.

### **8.2.3 Electrocardiograms**

- Single standard 12-lead ECG will be obtained as outlined in the SoA (see [Section 1.3](#)) using an ECG machine that automatically calculates the heart rate and measures PR, QRS, QT, and QTc intervals. The ECG should be recorded after 10 minutes of rest in the supine position.

### **8.2.4 Clinical safety laboratory assessments**

- See Appendix 2 ([Section 10.2](#)) for the list of clinical laboratory tests to be performed and to the SoA ([Section 1.3](#)) for the timing and frequency.
- The Investigator must review the laboratory report, document this review, and record any clinically relevant changes occurring during the study in the AE section of the CRF. The laboratory reports must be filed with the source documents. Clinically significant abnormal laboratory findings are those which are not associated with the underlying disease, unless judged by the Investigator to be more severe than expected for the participant's condition.
- All laboratory tests with values considered clinically significantly abnormal during participation in the study should be repeated until the values return to normal or baseline or are no longer considered clinically significant by the Investigator or Medical Monitor.
- If such values do not return to normal/baseline within a period of time judged reasonable by the Investigator, the etiology should be identified, and the Sponsor notified.
- All protocol-required laboratory assessments, as defined in Appendix 2 ([Section 10.2](#)), must be conducted in accordance with the laboratory manual and the SoA ([Section 1.3](#)).

- If laboratory values from non-protocol-specified laboratory assessments performed at the institution's local laboratory require a change in participant management or are considered clinically significant by the Investigator (eg, SAE or AE or dose modification), then the results must be recorded in the CRF.

### **8.3 ADVERSE EVENTS AND SERIOUS ADVERSE EVENTS**

#### **Adverse event of special interest**

An adverse event of special interest (AESI) is an AE (serious or nonserious) of scientific and medical concern specific to the Sponsor's product or program, for which ongoing monitoring and immediate notification by the Investigator to the Sponsor is required. Such events may require further investigation in order to characterize and understand them. Adverse events of special interest may be added, modified or removed during a study by protocol amendment.

For these AESIs, the Sponsor will be informed immediately (ie, within 24 hours), per SAE notification described in [Section 10.3](#), even if not fulfilling a seriousness criterion, using the corresponding pages in the CRF (to be sent) or screens in the e-CRF.

- Anaphylactic reactions
- Systemic hypersensitivity reactions
- Helminthic infections
- Any severe type of conjunctivitis or blepharitis
- Keratitis
- Clinically symptomatic eosinophilia (or eosinophilia associated with clinical symptoms)
- Significant ALT elevation
  - ALT  $>5 \times$  the ULN in participants with baseline ALT  $\leq 2 \times$  ULN;  
or
  - ALT  $>8 \times$  ULN if baseline ALT  $>2 \times$  ULN.
- Pregnancy of a female subject entered in a study as well as pregnancy occurring in a female partner of a male subject entered in a study with IMP/non-investigational medicinal product (NIMP)
  - Pregnancy occurring in a female participant entered in the clinical trial or in a female partner of a male participant entered in the clinical trial. It will be qualified as an SAE only if it fulfills 1 of the seriousness criteria
  - In the event of pregnancy in a female participant, IMP should be discontinued.
  - Follow-up of the pregnancy in a female participant or in a female partner of a male participant is mandatory until the outcome has been determined.
  - Abnormal pregnancy outcomes (eg, spontaneous abortion, fetal death, stillbirth, congenital anomalies, ectopic pregnancy) are considered SAEs.

- Symptomatic overdose (serious or nonserious) with IMP/NIMP
  - An overdose (accidental or intentional) with the IMP is an event suspected by the Investigator or spontaneously notified by the participant and defined as at least twice the intended dose during an interval of less than 11 days. The circumstances (ie, accidental or intentional) should be clearly specified in the overdose form.
  - An overdose (accidental or intentional) with any NIMP is an event suspected by the Investigator or spontaneously notified by the participant and defined as at least twice the maximum prescribed daily dose, within the intended therapeutic interval. “The circumstances (ie, accidental or intentional) should be clearly specified in the overdose form”.

The definitions of an AE or SAE can be found in Appendix 3 ([Section 10.3](#)).

Adverse event will be reported by the participant (or, when appropriate, by a caregiver, parent, surrogate, or the participant's legally authorized representative).

The Investigator and any qualified designees are responsible for detecting, documenting, and recording events that meet the definition of an AE or SAE and remain responsible for following up AEs that are serious, considered related to the study intervention or study procedures, or that caused the participant to discontinue the study intervention (see [Section 7](#)).

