For Study C, to be conducted in the omalizumab naïve population, approximately 150 participants will be randomized. This corresponds to approximately 75 participants who will be randomly assigned to each intervention arm. It is planned that approximately 5% of participants enrolled will be adolescents and up to approximately 5% of participants enrolled will be children  $\geq 6$  to  $<12$  years of age (both children and adolescents recruited in some selected countries). In Study A, overall 52% of participants received H1-AH at recommended doses as background therapy, and 45% of participants presented with angioedema at baseline. To maintain consistency between the study population in studies A and C, and reflect the real-life distribution of patients with angioedema and uncontrolled by both standard dose or maximal H1-AH therapy, it is planned that

Study C would include not more than approximately 50% of participants (n=75) having their H1-AH therapy at recommended doses (for more details please see [Section 6.1.2](#)), and not less than approximately 30% (n=45) but not more than approximately 45% (n=68) of participants presenting with angioedema at baseline.

It is anticipated that approximately 30%-40% of enrolled participants will have angioedema.

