### 1.3 SCHEDULE OF ACTIVITIES (SOA)

Procedures	Screening (2 to 4 weeks before Day 1)	Intervention period (Weeks)			Follow-up (12 weeks)	Notes
		0 (Day 1)	12	24		
Visit	1	2 a	3	4 (EOT) b	5 (EOS)	
Screening/baseline:						
Informed consent	X					
Medical history	X					
Prior and concomitant medication	X	X	X	X	X	Concomitant medication including rescue OCS taken since last visit will be collected throughout the study
Demographics	X					
Inclusion/exclusion criteria	X	X				
Patient e-diary training	X	X				
Randomization		X				
Study intervention						
Call IVRS/IWRS	X	X	X	X	X	
IMP administration			X c			IMP will be administered every other week except (for study A and study C) for children <30 kg and ≥15 kg where it will be administered every 4 weeks. The planned last dose is at Week 22 except (for study A and study C) for children <30 kg and ≥15 kg where it will be administered at Week 20. Participants (or their care givers) are allowed to perform IMP injections at home.
Dispense/Upload electronic diary d	X		X			Device is dispensed at Screening (including instructions for use). At the EOS, the e-diary is returned to the site.
Safetye						
Physical examination f	X	X		X	X	
Vital signs g	X	X	X	X	X	
Electrocardiogram (12 lead)	X			X		ECG to be locally collected and read

Procedures	Screening (2 to 4 weeks before Day 1)	Intervention period (Weeks)			Follow-up (12 weeks)	Notes
		0 (Day 1)	12	24		
Visit	1	2 a	3	4 (EOT) b	5 (EOS)	
Hematology, biochemistry, urine analysis h	X	X	X	X	X	
Hepatitis, HIV Serology, TB test i	X					
Pregnancy test j	Serum	Ur	Ur	Ur	Ur	In between visit urine pregnancy tests must be performed at home (Weeks 4, 8, 16, 20, 28, and 32)
AE reporting, including SAEs	X	X	X	X	X	
Pharmacokinetics and ADAe						
Serum PK samples for dupilumab concentration k		X	X	X	X	
Anti-dupilumab antibody k		X	X	X	X	
Biomarkerse						
Serum total IgE		X	X	X	X	
Basophil activation test (optional sub-study)		X	X	X		For participants (except pediatric participants in Studies A and B and all Study C participants) who decide to participate and provide consent for the optional basophil activation test.

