- c Loading dose on Day 1 of 600 mg (2 SC injections of 300 mg) followed by 300 mg every 2 weeks (q2w) regimen for adults and adolescents  $\geq 60$  kg OR 400 mg (2 SC injections of 200 mg) followed by 200 mg q2w for adolescents  $< 60$  kg and children  $\geq 30$  kg (Study A and Study C) OR 600 mg (2 SC injections of 300 mg) followed by 300 mg q4w for children  $< 30$  kg and  $\geq 15$  kg (Study A and Study C) OR matched placebo.
- d Electronic diary is used for daily recording of patient's answers to the urticaria activity score over 7 days (UAS7) and angioedema activity score over 7 days (AAS7) questionnaires as well as antihistamines medication use for the duration of the study. This device is dispensed at screening visit (Visit 1), including instructions for use. Electronic devices will be returned to the Sponsor after end of study (EOS). For urticaria control test (UCT), dermatology life quality index (DLQI [ $\geq 16$  years old]) /children's dermatology life quality index (CDLQI [ $\geq 6$  to  $< 16$  years old]), chronic urticaria quality of life questionnaire (CU-Q2oL), 5-level EuroQol 5-dimensional questionnaire (EQ-5D-5L [ $\geq 16$  years old]) /EuroQol 5-dimensional questionnaire youth (EQ-5D-Y [ $\geq 6$  to  $< 16$  years old]), patient global impression of change (PGIC), patient global impression of severity (PGIS), and missed school/work days questionnaires, the participant will fill in the questionnaires during their site visit on a tablet that will be provided to the site.
- e Assessments/procedures should be conducted in the following order: participant-reported outcomes (other than participant assessment of injection pain), Investigator assessments, safety and laboratory assessments (including sample collection for anti-drug antibodies (ADA), pharmacokinetic (PK), biomarker, and optional DNA and RNA), and administration of study drug.
- f Physical examinations will include skin, nasal cavities, eyes, ears, respiratory, cardiovascular, gastrointestinal, neurological, lymphatic, and musculoskeletal systems.

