of IL-4/IL-13 by dupilumab represents a novel therapeutic approach for CSU patients. In a small case series of patients who had concurrent AD and CSU and were resistant to omalizumab, treatment with dupilumab improved their urticaria. This further supports the rationale to target aberrant IL-4/IL-13 signaling with dupilumab in patients with CSU. As this is a novel therapy that acts further upstream than IgE-targeted therapies, the clinical trials proposed here will test the efficacy of dupilumab in patients who have failed anti-histamines alone or who have failed both anti-histamines and omalizumab. Efficacy in patients who were intolerant to omalizumab will also be assessed. The master protocol EFC16461 will include 3 studies in CSU patients who remain symptomatic despite the use of H1-AH treatment - 2 studies will be in patients who are omalizumab naïve (Study A and Study C) and the third study in patients who are intolerant or incomplete responders to omalizumab (Study B). The selected dosing regimen is dupilumab 300 mg every 2 weeks (q2w) with a loading dose of 600 mg for adults; 300 mg q2w with a loading dose of 600 mg for adolescents  $\geq$ 60 kg at screening OR 200 mg q2w with a loading dose of 400 mg for adolescents <60 kg at screening; and 200 mg q2w with a loading dose of 400 mg for children  $\geq$ 6 to <12 years of age with weight  $\geq$ 30 kg at screening OR 300 mg q4w with a loading dose of 600 mg for children  $\geq$ 6 to <12 years of age with weight <30 kg and  $\geq$ 15 kg at screening. This dose is expected to achieve concentrations in serum that saturate the IL-4/IL-13 receptor and hence it is expected to provide the maximum benefit and therefore to achieve the optimal benefit/risk ratio in this patient population.

LIBERTY-CSU CUPID Study A was completed and demonstrated that dupilumab at the above-mentioned dosing regimen is efficacious versus placebo in participants with CSU who remain symptomatic despite the use of H1 antihistamine (H1-AH) treatment (6). The trial included a total of 138 participants (132 adults, 4 adolescents and 2 children), with 68 participants in the placebo group and 70 participants in the dupilumab group.

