4.7.1 Extent of exposure

The extent of IMP exposure will be assessed by the duration of IMP exposure and compliance and summarized within the safety population.

Duration of IMP exposure

Duration of IMP exposure is defined as last dose date – first dose date + 15 days (or + 29 days for children <30 kg), regardless of unplanned intermittent discontinuations. If the date of the last dose of IMP is missing, the duration of IMP will be left as missing.

Duration of IMP exposure will be summarized descriptively as a quantitative variable (number, mean, SD, median, minimum, and maximum). In addition, duration of IMP exposure will also be

summarized categorically by numbers and percentages for each of the following categories and cumulatively according to these categories:

- >0 and \leq 2 weeks
- >2 and \leq 4 weeks
- >4 and \leq 8 weeks
- >8 and \leq 12 weeks
- >12 and \leq 16 weeks
- >16 and \leq 20 weeks
- >20 and \leq 24 weeks
- >24 weeks and \leq 24 weeks + 3 days
- >24 weeks + 3 days

Additionally, the cumulative duration of IMP exposure will be provided, defined as the sum of the duration of treatment exposure for all participants, and will be expressed in participant years.

Treatment compliance

A given administration will be considered noncompliant if the participant did not take the planned dose as required by the protocol. No imputation will be made for participants with missing or incomplete data.

Percentage of treatment compliance for a participant will be defined as the number of administrations that the participant was compliant divided by the total number of administrations that the participant was planned to take from the first administration of IMP up to the actual last administration of IMP.

Treatment compliance will be summarized quantitatively and categorically: <80%, \geq 80%.

Cases of overdose (defined as at least twice the intended dose during an interval of less than 11 days (or less than 25 days for children <30 kg) are considered an AESI and will be listed as such.

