4.7.1 Extent of exposure

The extent of IMP exposure will be assessed by the duration of IMP exposure and compliance and summarized within the safety population.

Duration of IMP exposure

Duration of IMP exposure is defined as last dose date – first dose date + 15 days (or +29 days for children < 30 kg), regardless of unplanned intermittent discontinuations. If the date of the last dose of IMP is missing, the duration of IMP will be left as missing.

Duration of IMP exposure will be summarized descriptively as a quantitative variable (number, mean, SD, median, minimum, and maximum). In addition, duration of IMP exposure will also be summarized categorically by numbers and percentages for each of the following categories and cumulatively according to these categories:

- >0 and \leq 2 weeks
- >2 and \leq 4 weeks
- >4 and \leq 8 weeks
- >8 and \leq 12 weeks
- >12 and \leq 16 weeks
- >16 and \leq 20 weeks
- >20 and \leq 24 weeks
- >24 weeks and \leq 24 weeks + 3 days
- >24 weeks + 3 days

Additionally, the cumulative duration of IMP exposure will be provided, defined as the sum of the duration of treatment exposure for all participants, and will be expressed in participant years.

Treatment compliance

A given administration will be considered noncompliant if the participant did not take the planned dose as required by the protocol. No imputation will be made for participants with missing or incomplete data.

Percentage of treatment compliance for a participant will be defined as the number of administrations that the participant was compliant divided by the total number of administrations that the participant was planned to take from the first administration of IMP up to the actual last administration of IMP.

Treatment compliance will be summarized quantitatively and categorically: <80%, \geq 80%.

Cases of overdose (defined as at least twice the intended dose during an interval of less than 11 days (or less than 25 days for children < 30 kg) will be summarized.

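### The protocol's overdose definition uses the two-weekly dosing interval for everyone, so a doubled maintenance dose in a child on four-weekly dosing can be an overdose in the SAP but not in the protocol

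*Protocol*

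**What the plan says.** Protocol section 8.3 lists symptomatic overdose among the adverse events of special interest (AESIs). For the investigational product, overdose is "defined as at least twice the intended dose during an interval of less than 11 days". The definition has no exception for regimen, age or weight. Section 8.4, on treating an overdose, refers back to 8.3 and gives no other interval.

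Not all participants are on two-weekly dosing. The protocol's schedule of activities makes an exception "for children <30 kg and ≥15 kg where it will be administered every 4 weeks", in Studies A and C. Its footnote c sets their regimen as "600 mg (2 SC injections of 300 mg) followed by 300 mg q4w for children" in that weight range. Section 6.1.1 gives dosing windows of 14 ± 3 days and 28 ± 3 days.

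Section 4.7.1 of the SAPs repeats the 11-day rule and extends it: "or less than 25 days for children <30 kg" for Study A and "or less than 25 days for children < 30 kg" for Study C. The Study B SAP has no such clause, and Study B enrols no children.

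**The concern.** The two documents classify the same dosing error differently, and sites work from the protocol. The adjacent rule in section 8.3, for non-investigational products, does follow the regimen: it refers to "at least twice the maximum prescribed daily dose, within the intended therapeutic interval". The rule for the study drug does not.

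The error is foreseeable. Most participants are on two-weekly dosing, and trained caregivers may inject children at home. A four-weekly child put by mistake on the two-weekly schedule would receive maintenance doses 11 to 17 days apart, all of which the protocol definition misses.

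As the protocol stands, the site would not have to:

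- classify the event as an overdose;
- notify it as an AESI within 24 hours if there were symptoms;
- follow section 8.4, which calls for immediate contact with the medical monitor and close monitoring for at least 98 days.

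The SAP cannot restore the missing AESI, because its AESI selection table (section 4.7.2) identifies symptomatic overdose from the site's own answers on the adverse-event form.

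**Working it through.** **Where the two limits come from** (windows from protocol section 6.1.1; shortest permitted gap = nominal interval − 3 days)

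- Two-weekly: 14 − 3 = 11 days, the protocol's figure.
- Four-weekly: 28 − 3 = 25 days, the figure in the Study A and C SAPs.
- Whole-day gaps that are under 25 but not under 11: days 11 to 24, which is 14 possible values.

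**Which dosing errors fall between the definitions** (child of 15 to <30 kg: 600 mg loading dose, then 300 mg every four weeks)

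| Error | Given ÷ intended | Protocol | Study A and C SAPs |
|---|---|---|---|
| Two maintenance doses under 11 days apart | (300 + 300) ÷ 300 = 2.0 | Overdose | Overdose |
| Two maintenance doses 11 to 24 days apart | (300 + 300) ÷ 300 = 2.0 | Not an overdose | Overdose |
| First maintenance dose given early after loading | (600 + 300) ÷ 600 = 1.5 | Not an overdose | Not an overdose |

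Only the middle row is in dispute.

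**How many children could be affected**

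- Study A randomized "132 adults, 4 adolescents and 2 children": 2 ÷ 138 = 1.45%. Their weights are not stated.
- Study C at the Study A rate (an assumption): 0.0145 × 150 = 2.2 children, about 1.1 on dupilumab under 1:1 allocation.
- Study C at its ceiling, where "up to approximately 5% of participants enrolled will be children": 0.05 × 150 = 7.5 children, about 3.75 on dupilumab.
- The share of children under 30 kg is not given. Taking it from none to all, Study C has 0 to about 4 dupilumab-treated children at risk.

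**Remaining follow-up after such an event** (end of study at Week 36)

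- From the planned last four-weekly dose at Week 20: 16 × 7 = 112 days.
- From an extra dose given by mistake at Week 22: 14 × 7 = 98 days.
- From an extra dose 24 days after the Week 20 dose, the latest that falls in the gap: 112 − 24 = 88 days.

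Routine adverse-event collection therefore covers most or all of the 98-day minimum in section 8.4, even if the event is never flagged.

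**The case against.** The difference in wording is not in dispute. The case against concerns consequence and cost.

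- **Intent.** No document says that 11 days was derived from the two-weekly window. It could be a deliberate short-exposure threshold, and these children receive 600 mg in one day as planned loading. That is fair as far as it goes. However, the SAPs add a regimen-specific limit for the same category of event, and both limits equal the shortest permitted gap for their regimen. An unexplained difference between the documents remains on either reading.
- **Purpose of the SAP clause.** It sits under extent of exposure and may be only a tabulation rule, which could be applied from dosing records. That would rescue the exposure summary, though the Study C SAP does not name its data source. It would not rescue the AESI row, site notification or section 8.4 handling.
- **Residual capture.** This stands. Dosing deviations are recorded, symptoms of a suspected overdose are adverse events whatever the interval, and serious events and the other AESIs are still notified within 24 hours. What is lost is urgent notification of a non-serious symptomatic event that is not another AESI, together with the overdose procedures.
- **Reach and cost.** The number of affected children may be zero, and the range above counts children at risk, not expected events. AESIs are changed by protocol amendment, which needs ethics approval, and Study C has been randomizing since 02 August 2022. This justifies bundling the change with other business but does not justify leaving the mismatch.

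**Conclusion.** The point holds: section 8.3 is wrong as written for the four-weekly regimen, and it disagrees with the Study A and C SAPs over gaps of 11 to 24 days between maintenance doses. It is a minor patient-safety and consistency point, desirable to correct and not critical. It does not show that any event has been missed. At most about 4 dupilumab-treated children in Study C are exposed to the gap, assuming that the ceiling on children is filled, allocation is even and every child weighs under 30 kg. The lower end of the range is zero. No event rate is available, so an expected number of events cannot be given. The design and the efficacy analyses are untouched.

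**What to change.** In the study-drug overdose definition in protocol section 8.3, after the 11-day limit, add: or less than 25 days for children under 30 kg on four-weekly dosing. Section 8.4 then needs no edit, because it relies on the definition in 8.3, and the SAPs already carry this limit.

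The cost is one phrase, made at the next amendment raised for another reason and subject to the usual ethics approval. Sample size, visits, forms and SAP text do not change. Sites would flag a few more events on the existing overdose form. There is no blinding cost, because the protocol already states that the dosing frequency in children is not blinded.
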